### 3.4 Safety Variables

- Adverse events (AEs)
- Standard safety laboratory tests (hematology, clinical chemistry, and urinalysis)
- Vital signs: respiratory rate, body temperature, blood pressure, pulse rate
- Complete physical examination: general appearance; head, eyes, ear/nose/throat, and neck; and lymphatic, cardiovascular, respiratory, gastrointestinal, musculoskeletal, neurological, and dermatological systems
- 12-lead ECG
- Chest imaging (x-ray or CT scan) findings

## 4. Pharmacokinetic Variables

- Trough (predose) plasma concentration ( $C_{trough}$ )
- Maximum plasma concentration ( $C_{max}$ )
- Time to  $C_{max}$  ( $t_{max}$ )
- Area under the plasma concentration versus time curve (AUC) from time zero to the time of last quantifiable concentration ( $AUC_{0-last}$ )
- AUC within a dosing interval ( $AUC_{tau}$ , where  $\tau = 12$  hours).

## 5. Analysis populations

### 5.1 All Enrolled Set

All patients who signed the informed consent form (ICF) will be included in the all enrolled set.

### 5.2 Intention-to-treat (ITT) Set

All randomized patients. Patients will be analyzed according to the treatment to which they were randomized.

### 5.3 Modified ITT (mITT) Set

All randomized patients who received at least one dose of study drug.

**CONFIDENTIAL**

Document Date: 29 Nov 2021

Page 11 of 34  
ST-AD-008 version 05

## Statistical Analysis Plan

Sponsor Name: Golden Biotechnology Corporation  
Sponsor Protocol ID: GH Covid-2-001

Covance Study ID: 000000203201

### 5.4 Per Protocol Set (PPS)

All patients from the ITT set who have no important protocol deviations during the study. Patients with important protocol deviations considered to have a major effect on efficacy shall be excluded from the PPS prior to database lock.

Protocol deviations are defined as any change, divergence, or departure from the study design or procedures defined in the study protocol. Important protocol deviations are a subset of protocol deviations and may significantly impact the correctness, accuracy, and/or reliability of the study data or that may significantly affect a Patient's rights, safety, or well-being. Prospective approval of protocol deviations to recruitment and enrollment criteria, also known as protocol waivers or exemptions, is not permitted. Section 5.4.1 details the deviations.

#### 5.4.1 Important Protocol Deviations Leading to Exclusion from the PPS Analysis

Only those important protocol deviations considered to have a major effect on efficacy will lead to complete exclusion of the patient from the PPS. For the purposes of this study, the following criteria have been identified as important protocol deviations leading to exclusion from the PPS as it is considered that the occurrences of any of these criteria might have an important influence on the primary efficacy endpoint. Patients will be assessed purely by comparison of their eCRF data with the criteria below.

**CONFIDENTIAL**

Document Date: 29 Nov 2021

Page 12 of 34  
ST-AD-008 version 05

## Statistical Analysis Plan

Sponsor Name: Golden Biotechnology Corporation  
 Sponsor Protocol ID: GH Covid-2-001

Covance Study ID: 000000203201

Type	Important Protocol Deviation Leading to Exclusion from the PPS	Method of Identification
Inclusion Criteria 2	patient aged under 18 or over 80.	Non-Programmable check of age collected during screening visit.
Inclusion Criteria 4	patient does not meet the condition of mild COVID-19 disease.	Non-Programmable check of the WHO COVID-19 Clinical Improvement Ordinal Scale collected during screening visit.
Inclusion Criteria 5	patient with Chest x-ray or CT scan inconsistent with pneumonia.	Non-Programmable check of the chest imaging result during the screening visit.
Inclusion Criteria 6	patient does not meet: onset COVID-19 symptoms within 2 weeks prior to randomization.	Non-Programmable check of COVID-19 symptoms assessment during the screening visit.
Inclusion Criteria 7	patient does not have SARS-CoV-2 infection confirmed by a PCR test, antigen, or any authorized commercial or public health assay.	Non-Programmable check of SARS-CoV-2 test result during the screening visit.
Exclusion Criteria 2	patient with concomitant life threatening condition, including but not limited to: requiring mechanical ventilation, acute respiratory distress syndrome, shock, or cardiac failure.	Non-Programmable check of the medical history.
Exclusion Criteria 3	patient with evidence of multi lobar consolidation pneumonia or cavities on chest x-ray or CT scan.	Non-programmable check of the chest imaging form during the screening visit.
Exclusion Criteria 4	patient with score of 5, 6 or 7 in COVID-19 Clinical Improvement Ordinal Scale.	Non-Programmable check of the WHO COVID-19 Clinical Improvement Ordinal Scale during the screening visit.
Exclusion Criteria 5	patient with medical history for the following pulmonary diseases: lung cancer, cystic fibrosis, empyema.	Non-Programmable check of the medical history.
Exclusion Criteria 6	patient with respiratory rate >30 respirations per minute.	Non-Programmable check of the vital signs at the screening visit
Exclusion Criteria 8	patient treated with other drugs thought to possibly have activity against COVID-19 within 7 days prior to enrollment or concurrently. Note: remdesivir or other authorized treatments for COVID-19 is allowed if considered SoC, if started prior to randomization or during the study.	Non-Programmable check of the prior medications.

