3. INVESTIGATION PLAN

3.1. Overall study design and plan description

This is a randomized, double-blind, placebo-controlled, Phase 2, proof of concept study in hospitalized patients with mild to moderate pneumonia due to COVID-19. As antroquinonol has shown antiviral and anti-inflammatory activity in preclinical studies, it is being planned to use for treatment in patients with COVID-19 infection.

Approximately 15 to 20 sites in the United States, and other countries based on the pandemic situation, are planned to enroll patients.

[figure not shown]
The main characteristics of hospitalized patients to be included in this study are: adult patients with onset of COVID-19 symptoms within 2 weeks prior to randomization.

The planned treatment duration is 14 days of administration of antroquinonol or placebo in combination with SoC therapy per local SoC policies. The total study duration is planned to be a maximum of 33 days (screening period up to 3 days, planned study treatment duration up to 14 days, follow-up/End of Study (EOS) assessments up to 28 ± 2 days after start of treatment).

A total of 174 patients are planned to be randomized in a 1:1 ratio to antroquinonol or placebo.

The study will consist of a sentinel cohort of 20 patients (10 patients randomized to antroquinonol and 10 patients to placebo), and an expansion cohort of 154 patients (77 patients in each treatment group). Enrollment will pause after the 20th patient in the sentinel cohort has started treatment, until the results of the interim analysis are known. Once the 20th patient in the sentinel cohort has completed 14 days of treatment, an unblinded Data Monitoring Committee (DMC) will assess the safety, tolerability, efficacy, and PK of 100 mg twice daily (BID) antroquinonol in COVID-19 patients in the sentinel cohort (interim analysis 1). The DMC will issue a recommendation to enroll patients for the expansion cohort, or to stop the study depending on the safety and futility assessment. Once the 80th patient has been enrolled and completed 14 days of treatment, the DMC will review safety, tolerability, and, efficacy data (interim analysis 2). Enrollment may be restricted at the 100th patient until the DMC has completed the assessment to prevent excessive enrollment. The DMC will continue to review safety and assess the risk/benefit profile on an ongoing basis.

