4.1. Inclusion Criteria

Patients must satisfy all of the following criteria at the screening visit unless otherwise stated:

1. Willing and able to provide informed consent.
2. Male or female patients between 18 and 80 years of age.
3. Oxygen saturation <94% in room air at screening.
4. Hospitalized with mild COVID-19 disease (not requiring oxygen therapy [WHO COVID-19 Clinical Improvement Ordinal Scale, score of 3] or requiring oxygen therapy by mask or nasal prong [WHO COVID-19 Clinical Improvement Ordinal Scale, score of 4]). Requirement of oxygen therapy by mask with reservoir to treat severe COVID-19 pneumonia is not allowed for enrollment.
Note: Hospitalized patients can also include patients admitted to centers conditioned as hospitals to treat COVID-19 patients.
5. Chest x-ray or CT scan consistent with pneumonia.
6. Onset of COVID-19 symptoms within 2 weeks prior to randomization.
7. SARS-CoV-2 infection confirmed by a PCR test, antigen, or any authorized commercial or public health assay (nasopharyngeal, oropharyngeal, or respiratory samples, not serology testing).
8. Male patients and female patients of childbearing potential must agree to use protocol-specified methods of contraception ([Appendix 4](#)).
9. Female patients of childbearing potential must have a negative pregnancy test at screening or pretreatment on Day 1.
10. Male patients must agree not to donate sperm from the first dose through 90 days after the last dose of study treatment; female patients of childbearing potential should refrain from donation of ova from Day 1 until 90 days after the last dose of study treatment.
11. Patient is, in the opinion of the investigator, willing and able to comply with the study treatment regimen and all other study requirements.

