8. SAMPLE SIZE AND DATA ANALYSES

8.1. Determination of sample size

The decision to include 20 patients in the sentinel cohort was chosen arbitrarily.

The sample size for the expansion group has been determined to provide evidence of proof of concept efficacy should the treatment prove effective. The primary endpoint and futility rules are based on assessments at Day 14 to enable rapid decision making, and the assessment at Day 28 will also be presented as a secondary endpoint.

The detailed assumptions are as follows, and the calculations include the patients from the sentinel cohort that were treated with the same dose used for the expansion cohort:

Alpha	0.2 (one-sided)
Power	80%
Drop-Outs assumed	2%
Endpoint	Odds of patient alive and respiratory failure free by Day 14
Effect Size	78% Placebo 89% Antroquinonol
Futility boundary shape	Manually chosen. Odds Ratio of 3.5 at interim analysis 1 in favor of placebo, and 1.2 at interim analysis 2 in favor of placebo. Equivalent to 4 patients not in respiratory failure on antroquinonol vs 7 on placebo at interim analysis 1, or 26 patients not in respiratory failure on antroquinonol vs 28 on placebo at interim analysis 2. Nonbinding
Efficacy boundary shape	None

In addition, the performance of the study under the following scenarios for the efficacy of antroquinonol were also considered:

Antroquinonol harmful	78% Placebo 67% Antroquinonol
Antroquinonol no effect	78% Placebo 78% Antroquinonol

The nonbinding decision rules of the interim analysis and stopping probabilities under:

Look #	Sample Size	Futility Stopping Boundary Odds Ratio	Cumulative Futility Stopping Probability		
			Drug harmful	No effect	Drug effective
Interim analysis 1	20	3.5	25%	17%	5%
Interim analysis 2	80	1.2	79%	44%	9%
Final	174	0.697			

The decision rules may be modified pending discussion with the DMC, but any modifications will still be considered nonbinding; therefore, no adjustment for the final alpha will be made.

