Protocol Version 3.1	29 March 2021	This version was updated to clarify and adapt to changes on management of COVID-19.
Protocol Version 3.0	11 March 2021	This version was updated to clarify and adapt to changes on management of COVID-19.
Protocol Version 2.0	02 September 2020	This version was updated based on the ‘study may proceed’ letter from the Food and Drug Administration (FDA) on Version 1.1, and addressed feedback from DMC and Investigators.
Protocol Version 1.1	01 June 2020	Submitted to the FDA in response to their questions.
Original Protocol Version 1.0	14 May 2020	Submitted to the FDA in response to their questions.

The primary changes in this amendment, along with the rationale for the/each change as appropriate, are:

1. **Section 4.1:**

- New inclusion criterion #3: Inclusion requirement of oxygen saturation <94% at room air at screening was added following the DMC recommendation to ensure the “sicker” of the mild/moderate patients can be enrolled.
- Current inclusion criterion #4 (previous inclusion criterion #3): Based on DMC and Investigator’s feedback, this criterion was modified to exclude patients requiring oxygen therapy by mask with reservoir for treatment of severe Covid-19 pneumonia.

2. **Section 7.2.3:**

- Edits made to allow samples to be obtained for local laboratories tests in case of delays in transportation of safety samples to the central laboratory.

3. **Section 7.2.4.2:**

- Based on site’s local practices, collection of non-oral body temperature (i.e., tympanic, rectal, axillary, and frontal) was also included.
- Peripheral capillary oxygen saturation (SpO_2) assessment was aligned with vital signs assessments. Data of fraction of inspired oxygen (FiO_2) will be collected along with partial pressure of oxygen (PaO_2) (if PaO_2 is done as standard of care).

4. Section 8.2:

- To be consistent with the statistical analysis plan (SAP), the Intention-to-Treat (ITT) set will be the primary analysis population for efficacy and the modified ITT (mITT) and Per Protocol Set (PPS) will be the supportive analysis populations for efficacy analysis.

5. Appendix 5:

- Schedule of assessments table and footnote 'e' were updated to include data to be captured for oxygenation and their assessments.
- SpO2 assessment was aligned with vital signs assessments.

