### 2.3 Sample Size

A total of 174 patients are planned to be randomized into the study:

- 20 patients in the sentinel cohort (10 patients in each treatment group)
- 154 patients in the expansion cohort (77 patients in each treatment group).

This enrollment level ensures 80% power to demonstrate proof of concept efficacy with one-sided alpha of 0.2.

The sample size is based on the following assumptions:

- The randomized allocation ratio is 1:1 between the antroquinonol group and the placebo group
- The proportion of patients alive and free of respiratory failure is approximately 78% on placebo vs 89% on antroquinonol

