### **7.6.3 Exploratory Efficacy Analysis**

Subgroup analyses on primary endpoint will be provided for the parameters of age at baseline ( $> 65$  years vs  $\leq 65$  years), sex, and remdesivir or other authorized treatments for COVID-19 use at baseline. The interaction between each mentioned parameter and the treatment effect will be added one at a time into the primary logistic model and the corresponding p-value for that interaction term will be provided.

The impact on efficacy of any new authorized treatments recommended as SoC for COVID-19 during the course of the study will also be evaluated using the same method as above.

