- e A complete physical examination (general appearance, HEENT, lymphatic, cardiovascular, respiratory, gastrointestinal, musculoskeletal, neurological, and dermatological systems) will be performed at screening. Vital signs (respiratory rate, temperature, blood pressure, and pulse rate) to be assessed during hospitalization, on discharge, ET/EOT and Follow-up/EOS visit (for site or in-person visits only). Pulse oximetry to measure SpO2 ( $>94\%$  on room air) will be collected in the eCRF during the study if done per standard of care. Height and body weight will be measured only at screening.
- f Chest x-ray or CT scan should show findings consistent with pneumonia due to COVID-19 and will be performed at Screening and either at hospital discharge, at ET of Study Treatment, or at ET of Study, whichever comes first (Note: only 1 scan must be done for hospital discharge, ET of Study Treatment, or ET of Study). Chest x-ray or CT scan does not need to be repeated at screening if performed as standard of care and done within 48 hours of diagnosis. Chest x-ray or CT scan is not required post discharge.
- g Serum pregnancy test is to be performed in female patients of child-bearing potential at a local (site) laboratory, during screening or pretreatment Day 1, discharge, and ET/EOT. Urine pregnancy test may be performed but must be confirmed with a serum pregnancy test (screening only). The Follow-up/EOS visit test will be a urine pregnancy test only (pregnancy test kit will be provided to the patient when discharged). Additionally, local/country regulations will be followed as applicable (eg., monthly pregnancy test after the last dose of study treatment in female subjects of childbearing potential).

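### The SAP's per-protocol exclusion list omits the SpO2 criterion added in protocol 4.0 and cannot detect the new reservoir-mask bar, and no analysis compares patients enrolled before and after the change

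*SAP*

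**What the plan says.** Protocol 4.1 (version 4.0) has a new inclusion criterion 3, "Oxygen saturation <94% in room air at screening", and adds to criterion 4 that patients who need a reservoir mask for severe pneumonia may not enter. The summary of changes that follows Protocol Appendix 7 says that criterion 3 "was added following the DMC recommendation to ensure the" sicker of the mild-to-moderate patients can be enrolled. It attributes the reservoir-mask rule to DMC and investigator feedback.

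SAP Appendix 1 gives the move to protocol 4.0 as the reason for SAP version 3 (29 November 2021). SAP 5.4.1 says that patients are judged for the PPS purely by comparing their eCRF data with its listed criteria. The inclusion rows are numbered 2, 4, 5, 6 and 7. The row for criterion 4 reads "patient does not meet the condition of mild COVID-19 disease", and its stated source is the WHO ordinal score at screening. In Protocol Appendix 7, score 4 is oxygen by mask or nasal prongs.

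The primary model (SAP 7.6.1) adjusts for baseline authorised COVID-19 treatment and age. SAP 7.6.3 states "Subgroup analyses on primary endpoint will be provided for the parameters of age at baseline", then adds sex and baseline authorised treatment, with new standard-of-care treatments handled the same way. SAP 7.6 makes the ITT set primary and the PPS supportive.

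SAP Appendix 2, footnote e, still says that SpO2 "will be collected in the eCRF during the study if done per standard of care". The current protocol schedule has a separate oxygenation row and fixed SpO2 visits.

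**The concern.** A per-protocol set is meant to show the result in patients who met the entry rules that bear on efficacy. The SAP table includes several rules that fix disease severity at entry, such as the WHO score and a respiratory rate above 30. Criterion 3 is a rule of the same kind, added expressly to change how sick the enrolled patients are. The table skips it although its own numbering shows that the authors worked from the version containing it. The other new rule is nominally covered but is checked with a tool that cannot see it.

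Separately, the population was redefined by amendment while the trial was running, and all patients are pooled. Pooling is valid for the overall ITT test. But a reader of the report will ask whether the effect looks similar under the earlier and the current entry rules, and nothing in the SAP answers that.

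**Working it through.** **1. The plan's own design figure.** Inputs: "A total of 174 patients are planned to be randomized in a 1:1 ratio to antroquinonol or placebo" (Protocol 3.1), so 87 per arm; "78% Placebo 89% Antroquinonol" (Protocol 8.1); "This enrollment level ensures 80% power to demonstrate proof of concept efficacy with one-sided alpha of 0.2" (SAP 2.3).

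- Odds ratio = (0.89/0.11)/(0.78/0.22) = 8.09/3.55 = 2.28.
- Variance of the log odds ratio = 1/(87×0.89×0.11) + 1/(87×0.78×0.22) = 0.1174 + 0.0670 = 0.1844, so SE = 0.429.
- Final boundary at one-sided 0.2 = exp(−0.8416×0.429) = 0.697, which matches Protocol 8.1.
- Simulation with both futility looks followed and 2% dropout gives 80.6% power, which agrees with the stated 80%.

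The design figure reproduces. The point does not rest on a sample-size error.

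**2. The two new rules against the SAP table.**

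| Protocol 4.0 rule | Row in SAP 5.4.1 | Stated check | Can a violator be found? |
|---|---|---|---|
| Inclusion 3: room-air SpO2 below 94% | None | None | No |
| Inclusion 4: score 3 or 4 | Yes | WHO score | Yes |
| Inclusion 4: no reservoir mask | Only through the general mild-disease wording | WHO score | Not by the stated check |

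**3. Two hypothetical patients enrolled under version 4.0.**

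- Patient A has a screening room-air SpO2 of 97% and WHO score 3. Criterion 3 is failed, no row applies, and the list is the sole test. The patient stays in the PPS.
- Patient B is on a reservoir mask and is recorded as score 4. The inclusion 4 check passes, and the exclusion 4 row covers only scores 5 to 7. The patient stays unless someone looks beyond the stated source.

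**4. Does another part of the SAP pick this up?** SAP 7.4 tabulates baseline SpO2 and SAP 7.7.8 summarises oxygenation, but both are descriptive. SAP 6.1 defines baseline as the last value before first dose. That may be a Day 1 reading, not the screening room-air value that criterion 3 uses. No model, subgroup or sensitivity analysis in SAP 7.6 uses SpO2, protocol version or enrolment period.

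**5. What a before/after comparison could deliver.** Let f be the share enrolled before 4.0 (not in the documents), with 78% and 89% in both periods. The variance of the difference in log odds ratios is 0.1844×(1/f + 1/(1−f)).

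- f = 0.5: 0.1844×4 = 0.738, SE 0.859. The 95% interval for the ratio of odds ratios runs a factor exp(1.96×0.859) = 5.4 each way.
- f = 0.25 or 0.75: 0.1844×5.33 = 0.983, SE 0.992, a factor of 7.0 each way.
- Within one half of the trial, SE = 0.429×√2 = 0.607. An odds ratio of 2.28 would have a 95% interval of about 0.69 to 7.5.

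The comparison is descriptive and will detect only gross inconsistency.

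**The case against.** The strongest reply is that little turns on this. The PPS is supportive and the primary ITT test does not use the list. The list is selective by design, many other criteria are also unlisted, and the SAP allows exclusions to be added before unblinding. Waivers are prohibited (Protocol Section 4), so violators may be few or none. A reservoir mask used for severe pneumonia arguably fails the mild-disease wording, and criteria needing clinical interpretation are reviewed before lock. The SAP did take up other 4.0 content.

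Most of this stands, and it limits the consequence. It does not remove the gap. The SAP gives no reason for leaving out criterion 3. The route for additions is for deviations not anticipated when the SAP was prepared, whereas criterion 3 dates from July 2021 and the SAP from November. The mild-disease wording helps only if the reviewer departs from the stated source.

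Three stronger readings are tempting, and the documents support none of them.

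- *The headline result understates the effect in the current population.* A reader might assume that 30–70% enrolled earlier, with 5–10% placebo failure against 22% later. At a constant odds ratio of 2.28 this gives a pooled risk difference of 5 to 9 points against 11. Neither input is in the documents, and Protocol 8.1 is not among the listed 4.0 changes, so 78% was not tied to the new criteria. The primary measure would also barely move. For example, with half enrolled earlier at 10% failure, placebo failure is 16.0% and active failure is (4.64%+11%)/2 = 7.82%, a pooled odds ratio of (0.160/0.840)/(0.0782/0.9218) = 2.25. Across those inputs it is 2.19 to 2.25.
- *Version 4.0 is simply an enrichment.* The SpO2 rule removes less hypoxaemic patients, but the reservoir-mask rule removes sicker ones. Earlier patients could include both kinds, so the net shift in risk is unknown.
- *Unblinded efficacy results drove the change.* The DMC is described as unblinded, but the stated purpose is to admit sicker patients, and nothing says that comparative data prompted it.

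**Conclusion.** The point holds for the supportive per-protocol set and for the missing consistency check. Followed literally, SAP 5.4.1 keeps version 4.0 patients who fail criterion 3, and its stated check for criterion 4 cannot identify reservoir-mask patients. The first is an explicit omission; the second is a gap in detection. No planned analysis shows whether the result is consistent before and after the entry criteria changed.

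The primary ITT test and its error rate are unaffected. No numerical size can be given, because the documents state neither the number of violators nor the number enrolled before 4.0. That some patients were enrolled before 4.0 is itself an inference, from the DMC and investigator feedback that prompted the amendment. The correction is worth making before unblinding because it is cheap and the list as written does not match the protocol it was written for.

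**What to change.** 1. In SAP 5.4.1, add a row for inclusion criterion 3: screening room-air SpO2 not below 94%, applied only to patients enrolled under version 4.0. Earlier patients did not violate it. Use the screening room-air value, not the SAP 6.1 baseline value.
2. For criterion 4, check the reservoir-mask rule against the screening oxygen-delivery or FiO2 record as well as the WHO score. Protocol 4.0 collects FiO2 at screening; the documents do not say whether the eCRF records the delivery device, so this should be confirmed.
3. In SAP 7.6.3, add one supplementary analysis of the primary endpoint by protocol version at enrolment (before 4.0 versus 4.0), which can be established for every patient. Report estimates with intervals. Give results by screening SpO2 (below 94% versus 94% or more) only where it was recorded. Do not use protocol version to fill in missing SpO2: earlier patients could well have had values below 94%, and the substitution would misclassify them.
4. As housekeeping, bring SAP Appendix 2 into line with the version 4.0 schedule.

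The cost is SAP wording, a manual check at PPS review, and one more model with a breakdown by SpO2. The PPS may lose a few patients. The estimates by version will be imprecise and confounded with calendar time and changing standard of care, so they should be read as a consistency check and not as a test.
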